5.2.1.2. MMRM with Log Transformation

The MMRM approach with a log transformation will be used for endpoints that are markedly skewed and positive. The natural log of the data at each visit will be used to calculate change from Baseline in the log transformed data, ($\log[\text{post-baseline value}] - \log[\text{baseline value}]$) which will be used as the dependent variable in the model. The LS means for each treatment group and the corresponding 95% CIs will be back-transformed (ie, exponentiated) resulting in percent of baseline (ie, percent of baseline = $[\exp(\text{LS mean})] * 100\%$) values less than 100% representing a decrease from baseline and values greater than 100% representing an increase from baseline

The differences in LS means and 95% CIs will be back-transformed (ie, exponentiated) resulting in a ratio of mean percentages of baseline where a ratio >1 indicates that fordadistrogene movaparovec has a larger increase relative to placebo.

5.2.1.3. Analysis of Covariance (ANCOVA)

The analysis of covariance (ANCOVA) model assumes that the error term has a normal distribution. The dependent variable will be the specific endpoint and the model will include a term for treatment group (as a categorical variable). Additional terms (eg, covariates and interaction effects) to be included in the model are specified in [Section 6](#).

The model-adjusted estimates for the endpoint for each treatment group will be provided using the LS means, standard error of each LS mean, and their 95% CIs calculated based on the average continuous covariate values. The differences in LS means (fordadistrogene movaparovec minus placebo) will be provided along with the corresponding standard error, two-sided p-value (unadjusted for multiplicity) and 95% CI (unadjusted for multiplicity).

5.2.2. Analyses for Time-to-Event Endpoints

Time-to-event endpoints will be summarized using the Kaplan-Meier (K-M) method and estimated K-M curves will be displayed graphically. Graphs will describe the number of participants at risk over time. Censoring definitions are provided in [Section 3.3.4](#) under the specific time to event endpoints.

5.2.3. Analyses for Proportions based on Number of Successes

Endpoints defined as the number of successes out of a possible number of tests for each participant at each timepoint will be analyzed using a generalized mixed model assuming a Binomial distribution with a logit link. For example, for the number of skills gained in the NSAA, the endpoint is the number of skills gained out of the number of skills that can be gained (score 0 at Baseline). The maximum likelihood estimation method with Newton Raphson iteration will be used. The fixed effect of treatment group (as a categorical variable) will be included in the model along with any covariates given in [Section 6](#). The effect of

treatment will be examined using the Wald chi-square statistic (CHISQ option). LS means and 95% CIs and the difference in LS means and 95% CIs will be estimated using the z-statistic, by defining degrees of freedom to be infinite in the model (DDFM=NONE). The inverse link transform (ILINK) will be applied to obtain the LS means on the original scale, which will represent average proportions of success.

The estimate of difference in LS means when back-transformed will represent an odds ratio comparing the odds of a success occurring between two treatment groups. In order to represent these proportions as meaningful counts of success, the proportions will be multiplied by the average of the baseline values of the number of tests across all participants, irrespective of treatment group. For example, for number of skills gained, the average baseline number of skills that can be gained will be calculated. Then the back-transformed LS means representing the proportion of successes for each treatment group will be multiplied by this average baseline value, to give a representation of the average number of skills gained for each treatment group, for the population in this study.

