2.3.1. Sample Size Determination

The sample size of 99 participants in the FAS (see Section 4) is based on the primary efficacy endpoint of change from Baseline at Week 52 in the NSAA total score. The above sample size (assuming 3 participants will drop out of the study prior to Week 52) will provide 98% power to detect a treatment difference (fordadistrogene movaparvovec minus placebo) of 3.0. These calculations are based on $\alpha=0.05$ (two-sided), a 3-look group-sequential design with a gamma family (-1) spending function to determine the efficacy boundary, a gamma family (-4) spending function for the non-binding futility boundary, a common standard deviation of 3.5, and using the normal approximation of the test statistic for the comparison between two means.

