5.1. Hypotheses and Decision Rules

For the primary endpoint, the null hypothesis is that there is no difference between fordadistrogene movaparvovec and placebo with respect to mean change from Baseline at Week 52 in the NSAA total score. The alternative hypothesis is that fordadistrogene movaparvovec is different from placebo with respect to mean change from Baseline at Week 52 in the NSAA total score.

The experiment-wise Type I error rate of $\alpha=0.05$ (two-sided) will be controlled using gatekeeping and fixed-sequence procedures for the primary and select secondary endpoints listed below. The hypotheses for the secondary endpoints are similar to those for the primary endpoint.

- Change from Baseline at Week 52 in the 10 meter run/walk velocity.
- Change from Baseline at Week 52 in the rise from floor velocity.
- Number of skills either improved or maintained at Week 52 based on the individual items of the NSAA.
- Number of skills gained at Week 52 based on the individual items of the NSAA.

If the null hypothesis for the primary endpoint is rejected, statistical testing proceeds to the hypotheses for the secondary endpoints; otherwise, formal statistical testing in the sense of controlling the experiment-wise Type 1 error rate stops and nominal p-values for secondary endpoints will be reported and interpreted accordingly.

The secondary endpoints will be tested in the order specified above. To maintain the study-wise type 1 error rate, the p value boundary for these secondary endpoint analyses will be the same as the primary analysis as detailed in IA SAP. If the null hypothesis for the first endpoint in the sequence is rejected, statistical testing moves to the next endpoint in the sequence. Statistical testing proceeds to subsequent endpoints in the sequence only if the null hypothesis for the previous endpoint is rejected. If a null hypothesis in the sequence is not rejected, formal statistical testing in the sense of controlling the experiment-wise Type I error rate is stopped for all endpoints later in the sequence and nominal p-values will be reported and interpreted accordingly.

The null hypothesis for the primary and secondary endpoints will be tested at Week 52 using the parameter and variance estimates from the mixed model repeated measures (MMRM) model or the generalized mixed model described in [Section 5.2](#).

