Appendix 5.3. Sample SAS Code for the Number of Skills Gained at Week 52 Analysis

```
/*save overall baseline mean as variable base_mean*/

proc sql;

  select avg(denomi) into: base_mean

  from adrs2 where ^missing(TRT01P);

Quit;

%put &base_mean;

proc glimmix data=adrs2;

  class TRT01P;

  model prop_skills = TRT01P agemodel / dist=bin link=logit chisq ddfm=NONE;

  lsmeans TRT01P / cl ilink ;

  lsmeans TRT01P / at agemodel=4 cl ilink ;

  lsmeans TRT01P / at agemodel=5 cl ilink ;
```

```

lsmeans TRT01P / at agetmodel=6 cl ilink ;
lsmeans TRT01P / at agetmodel=7 cl ilink ;
estimate 'Treat diff' TRT01P 1 -1 / cl ilink;
ods output LSMMeans=means4 estimates=est4;

run;

```

```

Data means5;

set means4 ;

extimate _MU_Gained=(MU)*&base_mean;

if agetmodel ^in (4, 5, 6, 7) & ^missing(TRT01P);

run;

```

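### The two alpha-controlled NSAA skills endpoints have no variance term for between-boy differences, and the SAP text, Appendix 1 and sample code describe different models

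*SAP*

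**What the plan says.** SAP Section 5.1 states: "The experiment-wise Type I error rate of $\alpha=0.05$ (two-sided) will be controlled using gatekeeping and fixed-sequence procedures". The third and fourth secondaries in the sequence are "Number of skills either improved or maintained at Week 52 based on the individual items of the NSAA" and "Number of skills gained at Week 52 based on the individual items of the NSAA". On the significance level it adds that "the p value boundary for these secondary endpoint analyses will be the same as the primary analysis as detailed in IA SAP".

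Four places describe the model for these two endpoints:

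- **Section 5.2.3.** Counts of successes out of a number of tests per participant "will be analyzed using a generalized mixed model assuming a Binomial distribution with a logit link". Estimation is by maximum likelihood, the treatment test is a Wald chi-square, and intervals use the z-statistic "by defining degrees of freedom to be infinite in the model (DDFM=NONE").
- **Section 6.2.3.1.** The model is again called mixed, but the only terms listed are treatment group and Screening age. The denominator is 17 for every boy for improved/maintained. For skills gained it is the boy's own number of items scored 0 at baseline.
- **Appendix 1.** The model is a generalized linear model; the word mixed is absent.
- **Appendix 5.3** (skills gained only). The statement is "model prop_skills = TRT01P agemodel / dist=bin link=logit chisq ddfm=NONE". The listing has no random statement, scale, weight or events/trials form. A denominator variable exists in the data set but is used only to average the number of gainable skills.

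Where the SAP wants a participant random effect it says so: Section 5.2.1.1 does this for the MMRM.

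**The concern.** A boy's items at Week 52 share his disease course, so they are unlikely to be independent. The SAP's own rules add to this. Under Section 2.2.2, after death, or after loss of ambulation with no NSAA done, all of a boy's items count as 0 together. Under Section 3.2, an item that is 0 at baseline and stays 0 is a failure for improved/maintained, so a boy's success rate depends on how many zeros he started with; the model has no baseline NSAA term.

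A binomial model with fixed effects only and a z reference takes its standard error from the binomial formula and never estimates the spread between boys. If that spread exceeds the binomial amount, the test rejects too often under the null, in a sequence that claims strict error control. The sample code drops the denominator and so leads to a different standard error. Two analysts, one following the text and one the code, could reach different conclusions on the same data.

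**Working it through.** **The plan's own figure.** The SAP gives power only for the primary endpoint (Section 2.3.1): 99 boys, 3 dropouts, 2:1 allocation, difference 3.0, SD 3.5, stated power 98%. With 64 and 32 boys, SE = 3.5 × √(1/64 + 1/32) = 0.758; 3.0/0.758 = 3.96; Φ(3.96 − 1.96) = 97.7%. The three-look design gives 97.0%. The figure reproduces. No figure is given for the skills endpoints.

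**Inputs that are assumptions.** The SAP gives no within-boy correlation ρ, no item-difficulty spread and no distribution of baseline zeros. Ranges are used below. Simulations used 64 and 32 boys, an age covariate, and 4000 null or 2000 alternative runs per setting.

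**1. Events/trials with no overdispersion term, 17 items.** The design effect is 1 + 16ρ, and type I error = 2 × [1 − Φ(1.96/√deff)].

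| ρ | deff | formula | simulated |
|---|---|---|---|
| 0 | 1.0 | 0.050 | 0.054 |
| 0.05 | 1.8 | 0.144 | 0.139 |
| 0.10 | 2.6 | 0.224 | 0.218 |
| 0.20 | 4.2 | 0.339 | 0.344 |
| 0.30 | 5.8 | 0.416 | 0.421 |

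If both interim analyses are run, the final nominal boundary is about 0.034-0.035. At 0.034 (z = 2.12) and deff 2.6, 2.12/√2.6 = 1.315, an error of about 0.19.

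**2. The same reading, skills gained** (simulated, success proportion 0.3).

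| Items at risk | ρ = 0.1 | ρ = 0.2 | ρ = 0.3 |
|---|---|---|---|
| 1-8 | 0.107 | 0.153 | 0.206 |
| 1-4 | 0.075 | 0.094 | 0.110 |

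**3. When item difficulty varies within a boy.** The binomial variance is then partly overstated. For 17 items, simulated type I error is 0.016, 0.046, 0.152 and 0.267 at boy-effect SDs of 0, 0.5, 1 and 1.5 on the logit scale. Inflation therefore needs net overdispersion.

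**4. One boy with every item set to 0.** For improved/maintained he adds 17p/(1 − p)/96 to the Pearson dispersion. At an assumed p = 0.80 this is 17 × 4/96 = 0.7.

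**5. As coded, if each record counts as one trial** (an assumption about the software). For skills gained, type I error is 0.0015-0.014. Power at ρ 0.1-0.2, against a sandwich analysis of events/trials:

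| log OR (assumed) | as coded | sandwich |
|---|---|---|
| 0.5 | 0.07-0.11 | 0.28-0.47 |
| 0.75 | 0.29-0.33 | 0.57-0.83 |
| 1.0 | 0.61-0.65 | 0.84-0.97 |

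**6. After the fix.** With a participant-level sandwich variance, simulated type I error is 0.049-0.062 for 17 items and 0.05-0.06 for skills gained. Power at log OR 0.75 and ρ 0.1 is 0.89 for 17 items (placebo proportion 0.8) and 0.83 for skills gained (1-8 items at risk, placebo proportion 0.3).

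**The case against.** The strongest reply is that Sections 5.1, 5.2.3 and 6.2.3.1 all say mixed, so a random term may be intended and merely unstated. The code is labelled a sample, and its response follows Section 6.2.3.1, which speaks of analysing proportions. This stands as far as intent goes: the SAP does not expressly choose an independence model. It does not repair the specification. The listed terms, Appendix 1 and the code all lack any such term.

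It is also fair that the inflation is conditional. The SAP quantifies neither boy-level heterogeneity nor item difficulty, and step 3 shows settings where the test is at or below 5%.

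A reader might infer more than the documents support:

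- **That the coded test is powerless.** Skills gained is the only endpoint coded, and there the loss is large but not total. Near-zero power (0.04-0.07 at log OR 0.75) would arise only if the code were reused for the 17-item endpoint, which the SAP does not show.
- **That text and code weight boys differently for both endpoints.** With 17 items for every boy, relative weights cannot differ; only the standard error does. Different weighting arises for skills gained alone.
- **That the planning assumption of "a common standard deviation of 3.5" reveals the overdispersion.** It does not. If 30% of items move one point, 12.25/(17 × 0.30) = 2.4. If a further 10% move two points, 12.25/(17 × 0.70) = 1.03. The answer is set by the invented pattern, and the SD belongs to a different variable.

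**Conclusion.** Wrong as written; it should be fixed. For two alpha-controlled endpoints the SAP specifies no estimate of between-boy variance, and its text, Appendix 1 and code do not describe one analysis. The size of the test as specified is right only if net overdispersion happens to be nil.

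Under the events/trials reading the error could be two to seven times nominal for improved/maintained (14-34% at ρ 0.05-0.20), and more modestly raised for skills gained. Under the coded reading, given one trial per record, the skills-gained test errs the other way. All these figures rest on assumed correlations, item counts and proportions.

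The consequence is bounded. The primary test is untouched, and the inflation reaches the error claim only once the primary and both velocity hypotheses have been rejected. It would be too strong to say that experiment-wise control certainly fails; the document does not supply the quantities needed to show that.

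**What to change.** Before unblinding, state one model identically in Sections 5.2.3 and 6.2.3.1, Appendix 1 and Appendix 5.3: a marginal binomial-logit model in events/trials form (skills over the boy's denominator) with a participant-level robust (sandwich) variance. A marginal model keeps the population-average proportions that the SAP multiplies into mean counts; a random intercept would make the odds ratio conditional and disturb that step. Remove the word mixed, or define it, including in Section 5.1, and align the estimation sentence in 5.2.3 with the chosen method.

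Give code for both endpoints and apply the same model to the rater-exclusion sensitivity analysis (6.2.3.2) and the age-strata analyses (6.5.1). Replacing the z reference with a t reference is optional.

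The cost is some wording and a few lines of code; the denominator variable already exists in the listing. The standard error will usually be larger than the naive binomial one, so some apparent power is given up.

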5.2.4. Global Statistical Test for Multiple Endpoints

To evaluate the treatment effect more comprehensively, a global statistical test (GST) will be conducted. The information from multiple functional endpoints will be aggregated in a single combined global test by aggregating test statistics from multiple endpoints into a single global test statistic. Because the units of the endpoints are different, the estimated group differences from MMRM will be standardized using a z score.

A permutation test will be performed to assess the chance of observing the mean z score assuming there is no treatment effect. The participants will be shuffled randomly between 2 treatment groups, and the mean observed z score will be calculated for each iteration. This process will be repeated 10,000 times. The standardized z score for each endpoint, mean observed z score across multiple endpoints, and p-value for the GST will be provided.

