2.3. Study Design

This is a Phase 3, global, multi-center, randomized, double-blind, placebo-controlled study to assess the safety and efficacy of fordadistrogene movaparvovec gene therapy in approximately 99 ambulatory male participants (in the FAS; see [Section 4](#)), ages ≥ 4 to < 8 years, with a genetic diagnosis of DMD who are on a stable daily regimen of glucocorticoids.

Eligible participants will be randomized into Cohort 1 or Cohort 2 in a 2:1 fashion and stratified by their age at Screening (< 6 or ≥ 6 years old). Study enrollment will be managed to ensure that no more than 55% of dosed participants are in either of the Screening age stratum. Enrollment will be assessed periodically, and if an imbalance is noted, enrollment of the overrepresented stratum may be paused until a more balanced distribution is achieved. In the context of this study, treatment will consist of two single intravenous infusions, one of fordadistrogene movaparvovec and one of placebo, with the timing and sequence as described below:

- Cohort 1 (approximately 66 participants): will receive a single dose of fordadistrogene movaparvovec on Day 1 (Visit 3) and a single dose of placebo at Day

DMB02-GSOP-RF02 4.0 Statistical Analysis Plan Template 01-Nov-2018

PFIZER CONFIDENTIAL

Page 14

TMF Doc ID: 98.03

390 (Visit 20). They will be followed for 5 years after the administration of the single dose of fordadistrogene movaparvovec. Total time on study will be approximately 5 years.

- Cohort 2 (approximately 33 participants): will receive a single dose of placebo on Day 1 (Visit 3) and a single dose of fordadistrogene movaparvovec at Day 390 (Visit 20), if they remain eligible. They will be followed for 5 years after the administration of the single dose of fordadistrogene movaparvovec. Total time on study will be approximately 6 years.

Figure 1. Study Schema

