2.3.3. Siblings

When ≥ 2 brothers meet all the study entry criteria, they will all be enrolled in the study simultaneously. One of the brothers will be defined as the “participant” and the other(s) will be defined as the “sibling(s)”. The sibling(s) will not be randomized but they will receive the same treatment with approximately the same timing (as long as the siblings were strictly separated from each other until both have received IP) and sequence based on the Cohort to which the participant is randomized. The sibling(s) will participate fully in the double blind study as a participant, complete all visits and evaluations, and comply with all protocol requirements. Data from the sibling(s) will not contribute to the main analyses of the primary and secondary endpoints. A supplementary analysis of the primary endpoint, NSAA, will include data from the sibling(s). Data from the sibling(s) will be included in all analyses of safety.

For analysis purposes, the “participant” and the “sibling” will be identified by specific ranges of randomization numbers. Two separate randomization lists will be created; one for participants age < 6 years and one for participants age ≥ 6 years. Each eligible participant will be randomized and receive a randomization number from the appropriate randomization list starting with the lowest randomization number. Sibling(s) will be manually assigned a randomization number in the IRT system by the IRT support team. The IRT support team will start at the end of the appropriate randomization list and working backward select the first un-assigned randomization number that will provide the same treatment as that randomly assigned to the participant.

- “Participants” will be those with a randomization number from 1-300 or 1001-1300, depending on their stratum assignment.
- “Siblings” will be those with randomization numbers from 301 to 996 or 1301-1996, depending on their stratum assignment.

If the participant is randomized within the first approximately 15 participants (with the potential to collect a maximum of 33 if needed) collecting muscle biopsies, muscle biopsies will be collected from him and his sibling(s). Biopsy data from the sibling(s) will be excluded from the main analyses of mini-dystrophin in this study, but will be included in supplementary analyses of the secondary endpoints.

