3.4. Baseline Variables

3.4.1. Covariates and Stratification Variables

- Baseline for the primary endpoint: Baseline NSAA total score is defined as the last non-missing NSAA total score collected prior to Year 1 IP administration.
- Baseline for secondary and exploratory endpoints: Baseline is defined as the last non-missing assessment collected prior to Year 1 IP administration.
- Screening age (years) covariate: The screening age covariate is defined as the participant's age (as calculated based on month and year of birth) on the day of the Screening visit. Screening age will be calculated to one decimal (eg, 7 years and 4 months will be 7.3 years).
- The participant's Screening age rather than Screening age stratum will be used in all efficacy analyses, unless specified otherwise.

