6.4. Global Statistical Test

The following endpoints will be included in the GST and will be considered as an exploratory analysis. The number of skills gained and number of skills improved or maintained will not be included in the GST as they are derived from the same 17 individual NSAA skills that contributed to the NSAA total score.

- Change from Baseline at Week 52 in the NSAA total score.
- Change from Baseline at Week 52 in the 10 meter run/walk test velocity.
- Change from Baseline at Week 52 in the rise from floor velocity.
- Change from Baseline at Week 52 in the 95th percentile of cadence.

Analysis set: FAS ([Section 4](#)).

- Analysis methodology: The GST will be conducted as described in [Section 5.2.4](#) by combining summary statistics for select functional endpoints listed above into a single global test statistic.
- For each endpoint, the estimated group difference from MMRM, the corresponding standard error, and standardized z score will be provided. The mean observed z score across multiple endpoints, and p-value for the GST will be provided.

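### The global statistical test's permutation is described without the screening-age strata used for randomisation; the effect is small and conservative, and one sentence mends it

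*SAP*

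**What the plan says.** SAP Section 5.2.4 forms a z score for each endpoint ("the estimated group differences from MMRM will be standardized using a z score"), averages the z scores, and refers the mean to a permutation distribution: "The participants will be shuffled randomly between 2 treatment groups, and the mean observed z score will be calculated for each iteration". It adds: "This process will be repeated 10,000 times". Strata are not mentioned.

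Randomisation is described in Section 2.3: "Eligible participants will be randomized into Cohort 1 or Cohort 2 in a 2:1 fashion and stratified by their age at Screening". Section 2.3.3 adds: "Two separate randomization lists will be created; one for participants age < 6 years and one for participants age ≥ 6 years". Blocking is not stated.

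Nothing elsewhere restricts the shuffle. Section 6.4 refers back ("The GST will be conducted as described in" Section 5.2.4), names four endpoints (NSAA total score, two velocities, 95th percentile of cadence) and calls the analysis exploratory. Appendix 1 says only that the p-value comes from permutation. Appendix 4 is empty, and the sample code in Appendix 5 does not cover the GST.

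The component MMRMs (Sections 6.1.1.1, 6.2.4.1 and 6.3.2) all include baseline, continuous screening age, and both interactions with visit. Section 3.4.1 sets the general rule: "The participant's Screening age rather than Screening age stratum will be used in all efficacy analyses, unless specified otherwise".

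**The concern.** A permutation test draws its validity from re-drawing labels in the way they were assigned. Where assignment is controlled within strata, the usual reference set holds the number per arm in each stratum fixed. An unrestricted shuffle also generates allocations in which the active arm is noticeably older or younger than the stratified lists would tend to give. If outcome depends on age in a way the statistic does not remove, those allocations widen the reference distribution and make the p-value too large.

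At stake is the GST p-value, the one new inferential result this analysis adds to the individual MMRMs. The wording is also loose enough that two programmers could obtain different p-values from the same data, although the default in Section 3.4.1 points towards shuffling everyone together.

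**Working it through.** **Inputs.** From the SAP: 99 in the FAS and 3 dropouts (Section 2.3.1), about 66:33 (Section 2.3), "no more than 55% of dosed participants are in either of the Screening age stratum", four endpoints (Section 6.4). Assumed: a 2:1 split fixed within strata, correlation between endpoints of 0.5 or 0.6, ages uniform over 4 to 8 years, and the form of the age effect. A Week 52 ANCOVA stands in for the MMRM.

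**The plan's own figure.** The SAP gives none for the GST. Its design power reproduces. With 64:32 completers, SE = 3.5·√(1/64 + 1/32) = 0.758, and Φ(3.0/0.758 − 1.96) = 97.7%. The three-look design gives about 97%, against a stated 98%. This confirms the design inputs only.

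**1. How far the split drifts.** With 66 active labels shuffled over strata of 50 and 49, the active count in the stratum of 50 is hypergeometric, with mean 33.3 and SD = √(50 · 2/3 · 1/3 · 49/98) = 2.36. Exactly 33 active occurs in 16.7% of shuffles, and within one of 33 in 47.3%. The 95% range is 29 to 38. With strata of 54 and 45 (54/99 = 54.5%, inside the cap) the two percentages are 16.9% and 47.9%.

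**2. How much of this reaches the statistic.** A linear age effect is removed exactly by the linear age term, so its size cannot matter. Take instead a step of δ SD at age 6.
- Best-fitting line: slope = (δ/2)/(16/12) = 0.375δ per year.
- What the line leaves: stratum means of ±(0.5 − 0.375)δ = ±0.125δ, so between-stratum variance δ²/64. Within strata the variance is 0.375²δ²·(4/12) = 3δ²/64. The total is δ²/16.
- Variance of the mean of four endpoints with correlation ρ: v = (1 + 3ρ)/4, which is 0.70 for ρ = 0.6 and 0.625 for ρ = 0.5.
- Ratio of SDs, unrestricted to within-stratum: √[(v + δ²/16)/(v + 3δ²/64)].

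For ρ = 0.6 this is 1.010 at δ = 1 and 1.035 at δ = 2. The effective critical values are 1.980 and 2.028, and type I error is 4.8% and 4.3% instead of 5%. For ρ = 0.5 it is 4.7% and 4.2%.

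**3. Simulation, age-adjusted z, two-sided 5%** (unrestricted vs within-stratum):

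| Run | Age effect | Type I error | Power |
|---|---|---|---|
| A | step 1 SD | 4.7% vs 5.1% | 74.2% vs 74.9% |
| A | step 2 SD | 4.3% vs 5.0% | 68.1% vs 69.6% |
| B | step 1 SD | 4.9% vs 5.4% | 76.7% vs 77.5% |
| B | step 2 SD | 4.3% vs 5.3% | 66.9% vs 69.8% |
| C | linear, any size | 5.5% vs 5.6% | not run |
| C | step ±0.5 SD (jump of 1 SD) | 5.3% vs 5.4% | not run |
| C | step ±1 SD (jump of 2 SD) | 4.7% vs 5.4% | not run |

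Run A has 3,000 null trials, 1,500 trials at a 0.5 SD treatment effect, and ρ = 0.6. Run C has 4,008 null trials and ρ = 0.5. The simulation SE of a single type I error is about 0.4 points in A and 0.35 in C. Within-stratum permutation is exact in this set-up, so departures from 5% in its column are noise; the informative quantity is the difference between the two shuffles in the same trials.

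**The case against.** The strongest reply is that 5.2.4 is silent rather than wrong: it neither requires nor forbids shuffling within strata. That stands as far as it goes, but the clarifying sentence is needed either way.

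Stronger readings are tempting, and the SAP does not support them.

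- *That the shuffle uses allocations the randomisation could not produce.* The unrestricted set contains every stratified allocation. How tightly two lists fix the split depends on blocking, which is not stated. With unblocked lists at the same 2:1 ratio, an unrestricted shuffle would itself be valid. The FAS also leaves out undosed boys, siblings and those meeting exclusion criterion 15 (Section 4), so the realised split need not be exactly 2:1.
- *That the 2:1 ratio is broken.* Shuffling labels keeps the arm totals; only the split by stratum drifts.
- *That false positives rise.* No run shows inflation from the unrestricted shuffle. The error is conservative.
- *That the loss is large.* Without age adjustment it would be: for a 1 SD step, type I error falls to 2.8% and power is about 70% vs 80% in run A. The SAP plans no such statistic.

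The assumed step is also generous. On the planning SD of 3.5, steps of 1 and 2 SD are 3.5 and 7.0 NSAA points, both above the 3.0-point design effect. Stratifying by age and fitting age-by-visit terms show interest in age, not evidence of a jump at 6.

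**Conclusion.** The point holds as a minor one. Read literally, Section 5.2.4 permutes without regard to the strata used for allocation, and no other section corrects this. Under an assumed step at age 6 of 1 to 2 SD, the cost is roughly 0.4 to 1 point of type I error in runs A and B (0.1 and 0.7 points in run C) and 1 to 3 points of power (0.7 to 0.8 at 1 SD, 1.5 to 2.9 at 2 SD). With a linear age effect there is no clear difference.

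These sizes rest on the assumed step, on a split held near 2:1 within strata, and on ANCOVA in place of the MMRM. The GST lies outside the testing sequence of Section 5.1, so no confirmatory conclusion is affected.

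**What to change.** Replace the shuffle sentence in Section 5.2.4 with wording such as:

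*Treatment labels will be permuted within each Screening age stratum (Randomization Group), holding the observed number of FAS participants per arm in each stratum fixed, and the mean z score will be recalculated for each of the 10,000 permutations.*

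Section 6.4 already refers to 5.2.4; Appendix 1 needs a matching phrase. Conditioning on observed counts, rather than on an assumed exact 2:1, keeps the test valid whether or not the lists were blocked and whatever the FAS exclusions did to the split.

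The cost is one sentence and a by-stratum step in the program. The stratum is already in the clinical database (Section 6.5.1), and strata of about 50 leave ample distinct permutations. The same edit could say whether the p-value is one- or two-sided and that the MMRMs are refitted at each permutation, since 5.2.4 states neither explicitly.
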